In our prior work at UCHealth EDs, we sought to reduce barriers to PDMP use and investigate the effectiveness of improved access to the PDMP and "mandated" consultation of the PDMP prior to signing an opioid e-prescription. We determined PDMP usage rates, prescription rates when the PDMP is used (or not), and patient outcomes. In the setting of already decreasing opioid prescribing, we found that one-click PMDP EHR integration is associated with an increase in the frequency of PDMP searches for ED patients who are prescribed an opioid. Unfortunately, still only a minority of ED patients receiving an opioid prescription were searched even after mandating use through an interruptive "best practice alert". "Mandated" use for our studies, is a relatively loose term. In order to not disrupt clinical workflows, information is presented as a "best practice alert" (BPA) in a pop-up window but providers can act on or bypass the alert. This design is required in order to ensure the tool does not impede patient care or the exercise of clinical judgment. Additionally, use across different ED sites and providers was highly variable, suggesting inconsistent care and the need for improvement.

After adjusting for site, provider and the patient's race/ethnicity and age, the predicted probability that a patient who received an opioid prescription would have been checked in the PDMP was only 0.218 (95% CI: 0.202 – 0.234) under the most stringent "mandatory" use criteria in our previous study.

Notably, there was a significant reduction in the probability that an opioid was prescribed as the number of opioids filled in the six months prior to the ED visit increased if the patient was searched in the PDMP (OR: 0.92 [95%CI:0.91-0.94] for every additional prescription). There was no such reduction for patients who were not searched (OR: 1.01 [95%CI:1.00-1.01] for every additional prescription). This suggests that reviewing the PDMP did have an effect on prescribing behaviors for high-risk patients.

We conclude that providing effective information on prior controlled medication use and risk assessment improves patient safety by decreasing high-risk prescribing. However, given poor compliance with "mandatory" consultation of the PDMP, it is clear that improvements are needed in information presentation to facilitate PDMP use. To address this

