2. Patients seeking care in the UCHealth system, who may receive an opioid prescription. The population will be limited to non-prisoners 12-89 years of age. Individuals with an active cancer diagnosis, sickle cell disease, or receiving specific end of life care are excluded. Pregnant women and decisionally challenged people will be included but are not considered a target population. No efforts will be made to include these individuals. Patients with limited literacy or limited English fluency will be included but are not considered a target population. Juveniles seen at providers included in the specialties of interest will be included (ages 12-17 inclusive) due to the inclusion of their health care provider. On the advice of pediatric toxicology experts, a cut point of 12 years of age is a clinically relevant age at which misuse of opioid analgesics and other controlled medications becomes a notable risk. However, no efforts will be made to target or enhance inclusion of juveniles. Pediatrics-only specialist offices will not be included in rollout of the CDS tools. Outcomes measures from juveniles will be examined separately from adults but may be included in the overall population if statistically appropriate.

C. Study Design and Research Methods

This will be a 1) cluster-randomized (by practice, as identified by a group of providers who work in the same department or set of departments within UCHealth) study for ambulatory/outpatient providers and 2) a randomized study (by provider) for emergency medicine and inpatient providers, with four study arms:

1. Arm 1: No change in practice
 - Providers are free to access the PDMP when prescribing via the existing integrated PDMP button.
 - This control group will enable monitoring of the secular changes in rates of controlled medication prescription within the UCHealth system.
 - In order to facilitate analysis of patient outcomes, CDS logic as in group 4 will run “silently” in this group such that risks are identified and recorded but not seen by the provider.
2. Arm 2: “Mandatory” use of the PDMP for all opioid prescriptions.
 - A best practice alert (BPA) will be triggered and fire when ordering an opioid prescription. The BPA will not appear (i.e. it will be suppressed) if the provider already reviewed the PDMP within the encounter. The BPA is shown in Figure 2 below.

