 - Although this condition is termed “mandatory” use, it is not a hard stop. The provider can easily close the window without consulting the PDMP and the prescription can be signed whether the PDMP has been consulted or not. The BPA will be built to track utilization of the BPA vs. bypass. Note: This has been deemed too interruptive for

[figure not shown]

Figure 2: Example BPA used in prior study.

ambulatory clinics and they will not be included in this arm.

3. Arm 3: CDS for high risk patients based on PDMP data
 - Based on initial interviews with providers (see 19-3063) CDS support will be designed to be supportive of provider workflows via interruptive alerts (BPAs) for high-risk patients only. No alerts will fire for patients without high risk indicators based on data in the PDMP or prescription history as shown in Epic. An example is given below. Exact phrasing may be modified during final testing in order to streamline appearance of the alert.
 - Again, BPA will be triggered upon entry of an opioid or benzodiazepine prescription and will fire only for patients determined to be at risk for controlled medication associated adverse events, misuse or overdose, based on logic built to identify high-risk characteristics. Definition of these risk characteristics is based on CDC guidelines and include: NarxCare opioid or overall overdose risk score (PDMP based) indicating the patient is in the highest ~5% of the population for controlled medication risk, initiating opioid treatment with an extended or long acting release formulation with no opioid usage in the previous 100 days, or information in the PDMP or EHR indicating overlapping opioid use or co-prescribing of a sedative with an opioid.
 - One-click access to the PDMP for all patients will be maintained as in other arms. If the provider reviews the PDMP during the encounter before prescribing, the BPA will be suppressed.

- As in Group 2, this is not a truly mandatory check and can be bypassed. BPA messaging was determined based on work with providers to deliver the most useful and clear information.
- The text displayed in the alert will be specific to the patient. BPA logic and phrasing is included in Appendix A.

[figure not shown]

Figure 3: Sample alert.

4. Arm 4: CDS for high risk patients based on PDMP and/or clinical characteristics

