The number of providers who choose to provide input on CDS design and implementation can only be very roughly estimated. The UCHealth system includes approximately 18,000 individual prescribers, not all of whom will see the alerts. Assuming 5% of individual prescribers choose to provide feedback through the survey available on the website, approximately 900 providers could provide feedback. No minimal response rate is required for significance as no hypotheses will be tested with these data. Survey data will be summarized via descriptive statistics only.

The driving factor in total enrollment is the patient outcome phase. As the tools will be active over the course of approximately 20 months, total patient counts over 20 months, rather than a power calculation, inform our assumptions about enrollment. Of the approximately 2.3 million individuals in the UCHealth system between the ages of 12 – 89, approximately 290,000 received at least one opioid prescription in the last 20 months. Approximately 906,000 individual patients were seen in the UCHealth system in the same time period.

The CDS tools used in this study will automatically query each patient record in order to obtain risk data, but data will only be seen by a provider in a fraction of cases. Based on the advice of privacy officials and COMIRB staff during the design of this study, all individuals queried are included as study participants, even if a provider does not see a study associated CDS alert for all

patients. As such, it is estimated that 950,000 patients will be included in this study. The number of patients queried will be monitored during the course of the study and updated as needed.

Data to be collected:

Variable	Definition	Importance
Prescriber/system data		
Overall controlled medication prescribing rate	Total number of opioid/sedative/stimulant prescriptions divided by total number of visits at each site and the hospital system	Measures the overall impact for each CDS tool
Individual provider controlled medication prescribing rates	Total number of opioid/sedative/stimulant prescriptions divided by total number of encounters for each provider	Measures the behavior and practice variation of individual prescribers for each CDS tool
Overall rate of PDMP use	Total number of times PDMP is accessed when opioid/sedative/stimulant prescriptions are written	Measures how readily providers obtain information for each CDS tool

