Provider specific rate of PDMP use	Total number PDMP searches for each provider, changes over time for each provider	Measures provider search behavior and variability changes for each CDS tool
Overall prescription rate after accessing PDMP	Number of times opioid/sedative/stimulant were prescribed after accessing the PDMP	Evaluate the impact of PDMP review on the decision to prescribe controlled medications
Provider demographics	Age, sex (M/F), years of employment (when available, data saved in EHR)	Evaluate variability in provider acceptance based on information stored in the EHR system.
Provider specific prescription rate after accessing PDMP	Total number of opioid/sedative/stimulant prescriptions divided by the number of times the provider accessed the PDMP for each provider	Evaluate provider variability in interpretation with and without decision support
Patient specific outcomes		
Patient demographics	Age, gender, ethnicity, insurance type	Description of patient population
Visit characteristics	Date of service [#] , service location, provider specialty, zip code	Evaluate visit for possible influences on patient and provider outcomes

Opioid prescription	Type, name, strength, number of pills, prescriber	Evaluate the effectiveness of the CDS tools
PDMP search completed	Yes/no	Evaluate the effectiveness of the CDS tools
Patient characteristics	Discharge diagnosis, past medical history, current co-morbid diagnoses, social history, other medications	Evaluate patient variability and other influences on prescribing/risk levels
CDS activation	Activation of CDS alert, which alert	Identify risk factors for patient as presented to prescriber
Prescriptions from PDMP	Type of medication (opioid, sedative, stimulant), date written [#] , date filled, [#] medication name, strength, formulation, # of pills prescribed, # of days supply, milligram morphine equivalents (MME), insurance type, pharmacy number	Evaluate patient outcome, needed for complete picture of prescription use
Non-UCHealth visits from All Payers Claims Data	ED visits, hospitalizations	Evaluate overall patient outcome, including unintended consequences of limitation of prescription pain medications
Provider Feedback		
Use of training materials and website	Usage (file access) over time	Measure of effectiveness of educational efforts

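### The provider-level rate of prescribing after PDMP access counts prescriptions signed without any check, so it falls when checking rises even if prescribing does not change (minor)

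*Combined protocol and SAP*

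**What the plan says.** Four rows or statements in the protocol bear on this. There is no separate SAP text on the variable.

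- **The provider-level row** (section IV.F, Data to be collected). The label refers to prescribing after PDMP access. The definition is "Total number of opioid/sedative/stimulant prescriptions divided by the number of times the provider accessed the PDMP for each provider", and the stated purpose is "Evaluate provider variability in interpretation with and without decision support".
- **The companion overall row** (same table). It is defined as "Number of times opioid/sedative/stimulant were prescribed after accessing the PDMP". It carries the restriction to prescriptions after access but has no denominator, although it is called a rate.
- **The individual provider prescribing rate** (same table). It is defined as "Total number of opioid/sedative/stimulant prescriptions divided by total number of encounters for each provider". It opens with the same numerator phrase as the provider-level row, and here the phrase plainly means all of the provider's controlled prescriptions.
- **The alert is not a hard stop** (section IV.C, Arm 2): "the prescription can be signed whether the PDMP has been consulted or not". The descriptions of Arms 3 and 4 also say that the alert can be bypassed.

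Section III reports from the team's earlier ED study that, under its strictest requirement to check, "the predicted probability that a patient who received an opioid prescription would have been checked in the PDMP was only 0.218" (95% CI 0.202 to 0.234).

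**The concern.** The label describes prescribing conditional on review. The formula does not: it sets everything the provider prescribed, checked or not, against the number of times that provider opened the PDMP. The denominator is the behaviour that the trial tries to change, since the first hypothesis in section I and the primary outcome in section IV.A both concern more PDMP checking among high-risk patients.

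A provider who starts checking more often and prescribes exactly as before gets a lower value. The row exists to show whether prescribers interpret PDMP information differently with and without decision support. If the formula is followed as written, a difference in checking, between providers or between alert conditions, would be reported under that heading. A programmer works from the definition column, and nothing elsewhere in the protocol limits the numerator.

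**Working it through.** The documents give no value for this variable, so there is no planned figure to reproduce. The check is algebraic, followed by illustrations.

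**Notation, for one provider**
- R = all controlled prescriptions
- A = PDMP accesses
- c = share of the R prescriptions that were preceded by an access
- q = prescriptions after access / accesses = cR / A, which is what the label describes

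**Identity.** As written, the variable is R / A. Since q = cR / A, it follows that R / A = q / c. The written ratio equals q only when c = 1, that is, when every prescription follows a check. Section IV.C allows c below 1 in every arm.

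**Response to more checking.** The proportional change in the written ratio is (1 + change in R) / (1 + change in A) − 1. The changes below are assumed, to show the range:

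| Change in accesses | Change in prescriptions | Change in written ratio |
|---|---|---|
| +25% | 0 | 1/1.25 − 1 = −20% |
| +50% | 0 | 1/1.5 − 1 = −33% |
| +100% | 0 | 1/2 − 1 = −50% |
| +100% | −10% | 0.9/2 − 1 = −55% |
| +100% | +10% | 1.1/2 − 1 = −45% |
| +100% | +100% | 2/2 − 1 = 0% |

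The ratio falls whenever accesses grow proportionally more than prescriptions.

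**Worked case.** Assume R = 1,000 and q = 0.5, and borrow c = 0.218 from section III.
- Before: 218 prescriptions follow a check, so A = 218 / 0.5 = 436. Written ratio = 1000 / 436 = 2.29. Restricted ratio = 218 / 436 = 0.50.
- After accesses rise 50% with q and R unchanged: A = 654, of which 327 lead to a prescription. Written ratio = 1000 / 654 = 1.53, a fall of 33%. Restricted ratio = 327 / 654 = 0.50.

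Prescribing after review did not change, and only the restricted ratio shows that. If c rose from 0.218 to 0.5 with q still 0.5, the written ratio would go from 2.29 to 0.5 / 0.5 = 1.00, a fall of 56%.

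**How common unchecked prescriptions may be.** If c were 0.218, the unchecked share would be 1 − 0.218 = 78.2% (76.6% to 79.8% over the confidence interval). The written ratio would be 1 / 0.218 = 4.59 times q (1/0.234 = 4.27 to 1/0.202 = 4.95). This shows that c can lie far below 1. It is not an estimate for this trial.

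**The case against.** The strongest reply is that this is drafting shorthand. The label says after access, the companion row says so too, and both stated purposes concern what happens after review. The hospital system measures in section IV.F also break prescriptions down by prescriber and by PDMP annotation, including those with no recorded check, so the team does not generally pool the two kinds. This makes an omitted phrase the likely cause. It does not correct the definition, which reuses a phrase that means all prescriptions elsewhere in the table.

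Several stronger readings are tempting but not supported:

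- **That the ratio is invalid because it can exceed 1.** The row is called a rate, not a proportion. The per-encounter rate can also exceed 1 when an encounter has several prescriptions.
- **That the trial's value will be inflated 4.6-fold.** The 0.218 is an adjusted, per-patient, opioid-only figure from an earlier ED study. This variable also covers sedatives and stimulants, and inpatient discharge and ambulatory settings.
- **That the trial's main results are biased.** The variable is not among the primary or secondary outcomes in section IV.A, and no hypothesis, model or sample size uses it.

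It is also fair to object that restricting the numerator does not fully isolate interpretation. In Arm 3 the "BPA will be triggered upon entry of an opioid or benzodiazepine prescription", so accesses prompted by an alert may tend to end in a prescription. In the control arm "risks are identified and recorded but not seen by the provider", so no access there is prompted by a visible alert. The corrected rate could therefore differ by arm for reasons other than interpretation. That stands, and it is why the fix labels the rate descriptive. Splitting reviews by route would not resolve it, because the control arm has no alert-prompted reviews to compare.

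**Conclusion.** The point holds as a minor definitional fault. The formula does not measure what its label and purpose state: it equals the post-access rate divided by the share of prescriptions that were checked, and it moves down as checking moves up. That identity needs no outside figure. The percentages in the table depend only on the assumed changes in accesses and prescriptions. The worked case also assumes q = 0.5, one access per checked prescription, and that the earlier study's 0.218 carries over. The real size in this trial cannot be known from the documents.

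The consequence is confined to one descriptive variable and its use to describe provider variability. The prescribing rates per visit and per encounter in the same table are unaffected.

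**What to change.** In the data table of section IV.F:

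1. Redefine the provider-level row as controlled prescriptions written after a PDMP access in the same encounter, divided by that provider's encounters with a PDMP access.
2. Give the companion overall row the same denominator, so that it becomes a rate.
3. Add one sentence stating that both rows are descriptive, because access is itself affected by the assigned arm, and that between-arm statements about prescribing rest on the per-encounter rate already listed, compared by assigned arm.

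The inputs are already listed in section IV.F. The hospital system measures give prescriptions by prescriber and by PDMP annotation or absence of a recorded check, and one-click PDMP use per visit. The patient-specific measures include PDMP use before each controlled prescription.

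The cost is two table rows, one sentence and minor programming. The team must also confirm that accesses not followed by a prescription can be linked to an encounter, since the new denominator depends on it.

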ATTACHMENT A
Provider/practice specialties included in data

Anesthesiology	Occupational Medicine
Behavioral Health	Ophthalmology
Brain and Spine	Oral Surgery
BREAST	Orthopedic Surgery
Breast Surgery	Otolaryngology
Burn Surgery	Pain Medicine
Cardiac Intensive Care	Physical Medicine and Rehabilitation
Cardiac Surgery	Plastic Surgery
Cardiothoracic Surgery	Primary Care
Dentistry	Psychiatry
Dialysis	Rehabilitation
EXEC HEALTH	Rheumatology
Family Medicine	Spine and Rehab Medicine
General Surgery	Sports Medicine
Gerontology	Surgical Intensive Care
Gynecology	Surgical/Trauma
Hand Surgery	Thoracic Surgery
INTEGRATED MEDICINE	Transplant
Internal Medicine	Urgent Care
INTERVENTIONAL CARDIOLOGY	Urology
Maternal and Fetal Medicine	VASCULAR
Medical Surgical	Vascular Surgery
Neurology	Womens Health
Neurosurgery	Workers Compensation
Obstetrics and Gynecology	Wound Care
